7.5.3.1 Analysis of clinical equivalence of test and reference treatments

A two-sided, continuity-corrected, 90% confidence interval on the Test-to-Reference difference for the proportion of patients with treatment success on the IGE will be constructed. Bioequivalence will be established if the 90% confidence interval for the difference is contained within the interval [-0.20, +0.20] for the PP population.

Analysis of bioequivalence will be performed both on the PP population and on the mITT population. The results on the PP population will be considered definitive and the results on the mITT population supportive.

7.5.3.2 Analysis of superiority to vehicle control

The evaluation of superiority will be conducted separately for the Test treatment versus the Vehicle treatment and for the Reference treatment versus the Vehicle treatment, comparing the proportions of patients with treatment success on the IGE. The analysis will be conducted using two-sided Fisher's exact test.

Superiority will be established if the success proportion for each active treatment is greater than, and statistically significantly different from ($p < 0.05$ for the Fisher's test) that of the

Vehicle for the mITT population. Analysis of superiority will be performed both on the PP population and on the mITT population. The results on the mITT population will be considered definitive and the results on the PP population supportive.

7.5.4 Analyses of IGE

Investigator Global Evaluation (IGE) expressed as severity grade 0 to 4 will be performed at each visit. For study enrollment, the patient must have an IGE rosacea severity score of 3 at Baseline visit.

Number and percentage of patient at each IGE severity grade will be tabulated by visit. In addition, a shift table for changes in IGE grades from Baseline to each post-baseline visit will be created. This analysis will be performed for both mITT and PP populations.

7.6 Safety Analyses

7.6.1 Adverse Events

Adverse Events will be coded using the MedDRA, Version 18.0, AE coding system for purposes of summarization.

Only Treatment Emergent Events (TEAEs) will be used for the summary analysis. An AE will be considered as treatment-emergent if the time of onset is after the time of the first study drug administration or if it increased in severity during the study period. AEs with unknown start dates will be counted as treatment-emergent unless the AE resolution date is prior to the study drug start date. If the start date is partially missing, then month and year (when available) will be used to determine if the event occurred prior to or post dosing.

A summary of the frequencies (number and percentage of patients) of TEAEs, serious TEAEs (AEs with missing seriousness will be treated as serious), treatment-related TEAEs will be presented by system organ class and preferred term. Adverse events will also be analyzed by their severity (Mild, Moderate, Severe). In case the severity was not assessed, the most conservative result – severe will be chosen for the analysis.

A TEAE is termed as treatment-related if it is recorded as definitely, probably, or possibly related to the study medication on the CRF. In case the relatedness was not assessed, the most conservative result – related will be chosen for the analysis.

A patient experiencing the same AE multiple times will only be counted once for that preferred term. Similarly, if a patient experiences multiple AEs within the same system organ class, that patient will be counted only once in that system organ class. All AEs will be listed in alphabetical order of SOC and preferred terms.

An overall summary will include, by treatment group and overall, the number of TEAEs and the number and percentage of patients reporting at least 1 TEAE in the following categories:

- Any TEAE,
- Treatment-related TEAE,
- Serious TEAE,
- TEAE leading to discontinuation of the study medication.

The following TEAE frequency tables will be prepared summarizing the overall number of TEAEs, the number and percentage of patients reporting at least one TEAE by MedDRA SOC and PT:

- All TEAEs,
- TEAEs by Severity,
- TEAEs by Relationship to Study Medication.

Additionally, TEAEs will be summarized by the preferred terms in the descending order of frequency in the total treatment group. In this table a p-value from Fisher's exact test comparing event rates between the Test and the Reference treatment groups will be provided for those preferred terms that have frequency > 1% in either Test or Reference group.

All information pertaining to adverse events noted during the study will be listed by patient, detailing verbatim, preferred term, system organ class, start date, stop date, intensity, outcome, action taken, and causal relationship to the study drug. The adverse event onset will also be shown relative (in number of days) to the date of first administration of the study medication. In addition, the adverse event duration (if AE Stop Date is available) will be evaluated as below and presented (in number of days).

$$\text{AE Duration} = \text{AE Stop Date} - \text{AE Start Date} + 1$$

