Superiority of the efficacy of the test treatment over that of the vehicle will be demonstrated if the test success proportion is greater than, and statistically different from ($p<0.05$) that of the vehicle by two-sided Fisher's exact test. The superiority of the efficacy of the reference treatment over that of the vehicle will be demonstrated in an identical manner.

Analysis of application site reactions

A descriptive analysis comparing the application site reactions for each treatment group will be conducted to ensure that the test product is not worse than the reference product with regard to the expected and unexpected application site reactions.

Safety Analyses

Safety analyses will be conducted on the safety population. Incidence of all adverse events reported during the study will be coded using the MedDRA dictionary and summarized by treatment group, body system, severity, preferred term, and relationship to study drug. In addition, an evaluation will be conducted of the comparability of the test and reference treatments in regard to any treatment emergent adverse events that occur in 5%, or more, of the patients in either test or reference treatment group.

The report of AEs will include date of onset, description of the AE, and date of resolution.

Concomitant medication

The start and stop date of concomitant medication use during the study will be provided in the data listings in addition to the reason for the medication use.

Demographics and Baseline/Randomization Characteristics

Demographic and baseline/randomization characteristics will be compared for the mITT, PP, and Safety populations. Continuous variables will be analyzed with an analysis of variance with factors of treatment and investigational site. Categorical variables such as gender, ethnicity, and race will be analyzed with a Cochran-Mantel-Haenszel test, stratified by investigational site.

Summary of patients who terminate prematurely

Reasons for premature termination will be summarized by treatment group.

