12.5.4 Safety Analyses

Safety analyses will be conducted on the safety population. Incidence of all adverse events reported during the study will be coded using the Medical Dictionary for Regulatory Activities (MedDRA) dictionary and summarized by treatment group, body system, severity, preferred term, and relationship to study drug. In addition, an evaluation will be conducted of the comparability of the test and reference treatments in regard to any treatment emergent AEs that occur in 5%, or more of the patients in either test or reference treatment group.

The report of AEs will include date of onset, description of the AE, and date of resolution.

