7. STATISTICAL METHODS OF ANALYSIS

7.1 General Principles

The statistical analyses will be performed by [REDACTED], under the direction of the Sponsor, Actavis Laboratories UT, using SAS Version 9.3(or higher). All tables, figures, and listings will be produced in the landscape format.

In general, all data will be listed by treatment group, patient and visit/time point where appropriate. The summary tables will also be stratified by, or have columns corresponding to, treatment group.

All patients will be identified by their unique patient numbers. Data from the screen failures will not be included in tables, listings, or figures.

The total number of patients in the study group (N) under the stated population will be displayed in the header of summary tables.

Data will be summarized using descriptive statistics for continuous variables. Unless otherwise stated, descriptive statistics will include number of patients, mean, standard deviation, minimum, median, and maximum. The minimum and maximum statistics will be presented to the same number of decimal places as the original data. The mean and median will be presented to one more decimal place than the original data. The standard deviation will be presented to two more decimal places than the original data. The number of missing observations will be presented only if non-zero.

In summary tables of categorical variables, counts, and percentages will be used. The count [n] indicates the actual number of patients in a particular category, which should always be less than or equal to the total number of patients in the respective study group with known (non-missing) category [N]. Percentage will be obtained by: $\% = n/N*100$. Unless otherwise stated, all percentages will be expressed to one decimal place.

All statistical tests will be two-sided at a significance level of $\alpha = 0.05$, unless otherwise indicated. No adjustment will be made for multiplicity.

Relative days will be calculated relative to date of first dose of study medication. In general, relative days will be calculated as follows only when the full assessment date is known (i.e., partial dates will have missing relative days).

For assessment on or after the day of first dose of study drug:

Relative Day = Date of Assessment – Date of First Dose of study Drug+1.

For assessment before the day of first dose of study drug:

Relative Day = Date of Assessment – Date of First Dose of study Drug.

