8. CHANGES FROM PROTOCOL-SPECIFIED ANALYSES

There are no changes from the protocol-specified analyses.

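### The SAP gives only a Fisher p-value, at a different threshold, for the protocol's Test/Reference adverse-event comparability evaluation, and no effect estimate or interval

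*SAP*

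**What the plan says.** Protocol 12.5.4 (Safety Analyses) states that "an evaluation will be conducted of the comparability of the test and reference treatments" and limits it to "treatment emergent AEs that occur in 5%, or more of the patients in either test or reference treatment group". The synopsis repeats the threshold: "treatment emergent adverse events that occur in 5%, or more, of the patients in either test or reference treatment group". Neither place names a test, an estimate, a margin or a decision rule.

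SAP 7.6.1 (Adverse Events) plans a table of preferred terms in descending frequency, in which "a p-value from Fisher's exact test comparing event rates between the Test and the Reference treatment groups will be provided". The column is not filled for every term; the SAP restricts it by a frequency cut-off: "for those preferred terms that have frequency > 1% in either Test or Reference group". The section mentions neither a 5% criterion nor comparability, and it does not say how the p-values are to be read. Its other outputs are event counts and numbers and percentages of patients by treatment group: overall, by system organ class and preferred term, by severity and by relationship.

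SAP 7.1 sets the general rule ("All statistical tests will be two-sided at a significance level of" 0.05) with no multiplicity adjustment. SAP 8 says: "There are no changes from the protocol-specified analyses".

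**The concern.** There are two linked gaps.

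- **Undeclared difference.** The protocol's threshold is 5% or more and the SAP's is above 1%, yet SAP 8 reports no departure.
- **Tool and question do not match.** The protocol asks whether two products are comparable. The SAP's only inferential answer is a test of the hypothesis that they do not differ. Failing to reject that hypothesis is weak evidence of similarity when events are uncommon. The size of the difference, and how large an excess the data can exclude, are not reported.

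For both efficacy endpoints the same SAP handles equivalence with a confidence interval set against limits (SAP 5, 7.5.2.1 and 7.5.3.1). Safety of the generic beside the reference is part of the stated objective (Protocol 10, SAP 2). At stake is whether the report can say anything quantitative about the largest excess on Test that the data still allow.

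**Working it through.** The documents state no power, margin or error rate for the adverse-event comparison, so there is no figure of the plan's to reproduce.

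**Inputs**
- Randomized: 924 at 1:1:1 (Protocol 12.1, SAP 3.2), so 924 / 3 = 308 per arm. Using 308 for the Safety population is an assumption and an upper value, because SAP 6.1 excludes randomized patients with neither evidence of dosing nor any data after Visit 1. Fewer patients would lower power.
- Test: two-sided Fisher exact, p < 0.05 (SAP 7.1 and 7.6.1).
- Event rates: not given in the documents. The rates below are illustrative.

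**Step 1: what the two thresholds select**
- Above 1%: 0.01 × 308 = 3.08, so at least 4 patients in an arm.
- 5% or more: 0.05 × 308 = 15.4, so at least 16 patients in an arm.

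Every term that meets the protocol's criterion also meets the SAP's. The SAP adds terms with 4 to 15 patients in the more affected of the two arms.

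**Step 2: chance that the test misses a true difference**

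Power = Σ over (x, y) of Bin(x; 308, p_T) × Bin(y; 308, p_R) × I[Fisher p(x, y) < 0.05], by exact enumeration.

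| Reference rate | Test rate | Power | Missed |
|---|---|---|---|
| 5% | 8% | 0.269 | 73% |
| 5% | 10% | 0.607 | 39% |
| 10% | 15% | 0.420 | 58% |
| 2% | 4% | 0.235 | 76% |
| 1% | 3% | 0.317 | 68% |

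The first three rows concern terms the protocol's criterion would pick up. The last two concern terms that only the SAP's lower cut-off adds.

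**Step 3: a result at the protocol's threshold**

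Take 16 patients on Reference and 29 on Test. This is the largest Test count that stays non-significant against 16.
- Rates: 16/308 = 5.19% and 29/308 = 9.42%. Ratio 29/16 = 1.8.
- Fisher p = 0.062.
- Difference: 13/308 = 4.22 points.
- Wald standard error: √(0.0942 × 0.9058/308 + 0.0519 × 0.9481/308) = 0.0209.
- 95% CI: 4.22 ± 1.96 × 2.09 = +0.1 to +8.3 points.

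The p-value would pass without a flag, while the interval shows an excess of up to 8.3 points still compatible with the data. The Wald interval here just excludes zero although Fisher's p exceeds 0.05. The two methods can disagree at the margin because Fisher is conservative, so the interval method should be named in advance.

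A less extreme case is 15 versus 26 patients (4.9% versus 8.4%): p = 0.105, difference 11/308 = +3.6 points, 95% CI −0.4 to +7.5. The term qualifies for the protocol's evaluation because the Test rate exceeds 5%.

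**Step 4: false positives**

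The exact size of the Fisher test at n = 308 is 1.3% when both rates are 1% and 3.2% when both are 5%, below the nominal 5%. Chance findings among rare terms are therefore fewer than a count of tests at 0.05 would suggest.

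**The case against.** The strongest reply is that the SAP never says comparability is judged by these p-values. It says only that they will be provided in a frequency table. A reader might infer a rule that p ≥ 0.05 means comparable, since no other comparative statistic for adverse events is specified, but no such rule is written. That part of the reply stands.

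It also stands that:
- the Fisher column is not the only comparison. Counts and percentages by arm would show an imbalance such as 16 versus 29, and local reactions have their own severity and shift tables (SAP 7.6.2), in line with the descriptive plan in Protocol 12.5.3;
- the 1% cut-off widens the protocol's set. A reader might infer that a required analysis has been dropped, but Step 1 shows that no 5% term is lost;
- a doubling from 5% to 10% would be detected 61% of the time, so a non-significant result there is a substantial possibility and not the expected one;
- unadjusted testing is openly declared, and Step 4 shows that false positives are a weak complaint;
- the table shells are in a separate document (SAP 9) that was not available, so columns beyond the SAP text cannot be excluded.

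None of this supplies the missing piece. The protocol promises an evaluation of comparability, and the SAP text specifies neither an estimate of the Test/Reference difference nor its uncertainty.

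**Conclusion.** The point holds as a minor one. The threshold difference is plain in the text and undeclared. The SAP names no comparability evaluation for adverse events, and the one inferential comparison it gives cannot support comparability. The size of the weakness, on 308 per arm and illustrative rates, is a miss probability of about 73% for 5% versus 8% and about 39% for 5% versus 10%. A non-significant result can coexist with an interval reaching +8.3 points.

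The exact percentages depend on those assumptions. The principle that non-significance does not show similarity does not. The documents do not support saying that the SAP equates non-significance with comparability, that a protocol-required term goes unanalysed, or that the p-values must be removed. The primary equivalence and superiority conclusions are not touched.

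**What to change.** 1. In SAP 7.6.1, add the comparability evaluation the protocol promises: for each preferred term at 5% or more in either Test or Reference, report the Test-minus-Reference risk difference with a 95% confidence interval, and name the interval method.
2. If the Fisher p-values for terms above 1% are kept, label them descriptive and state that non-significance is not evidence of comparability.
3. In SAP 8, record that the p-value table uses a threshold above 1% where the protocol's evaluation uses 5% or more.

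The cost is one extra table column and a few sentences, with no new data. It is best settled before the database is locked and treatment assignments are unblinded.

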7.6.2 Signs/Symptoms of Local Irritation

At each study visit, beginning with Visit 1, patients will be evaluated for any signs and symptoms of local irritation (application site reactions), including erythema, dryness, scaling, pruritus, burning/stinging and edema. Baseline values will be used for comparative purposes against the scores documented at subsequent visits for each treatment group. Each patient will be assigned a severity score by an Investigator based on the scale as presented in [Appendix 11.3](#).

Number and percentage of subjects with each severity will be presented by visit and by symptom. Additionally, the shifts from baseline in irritation score will be tabulated by site, treatment, symptoms and scheduled post-baseline visits. The denominator for the proportions will be the number of patients with evaluated signs and symptoms both at baseline and at given visit.

7.6.3 Exposure to Product

The patients will be instructed to use the diary to document all doses taken by checking the yes or no box for the appropriate date and am/pm time. The date(s) and reason for each dosing noncompliance must be recorded.

Compliance with scheduled application of IP will be determined from the patient's diary as $[Number\ of\ recorded\ applications] / [Planned\ number\ of\ applications] * 100\%$, where Planned number of applications is 168.

Number of missed doses will be calculated as follows. The number of doses missed in the dosing period (between the first and the last study drug application) will be taken directly from the CRF. Additionally, number of doses missed outside of the dosing period is the number of missed dosing times between the date and time (AM/PM) of the last dose and the date and time when the subject would have reached the required 168 doses (i.e. the date and time (AM/PM) of the first dose plus 84 days, inclusive)..

Patients who have more than 6 consecutive missed doses will be considered non-compliant and will be excluded from the PP population. For the dosing period >6 consecutive applications will be collected directly on the eCRF. Additionally, patients will be considered having >6 consecutive missed doses if after the dosing period patients missed more than 6

dosing times after their last dose and prior to the morning of Visit 4 date or the date and time (AM/PM) when they would have reached the required 168 doses, whichever occurs earlier. Patients can be additionally excluded from the PP population due to non-compliance, if the Investigator's and Sponsor's review of their dosing times suggests a clinically meaningful departure from a twice-daily dosing pattern.

Patients will be considered compliant if they apply at least 75% and not more than 125% of doses, with no more than 6 consecutive missed doses. The compliance will be analyzed using the descriptive statistics by treatment group. The proportion of compliant vs. non-compliant patients will be tabulated for each treatment.

Duration of exposure will be calculated as Date of last use of study medication – Date of first use of study medication + 1. Duration of exposure will be summarized descriptively by treatment group.

Compliance and duration of exposure will be summarized for the Safety and mITT populations.

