6.3 Per Protocol Population (PP Population)

The PP population includes all mITT patients who apply 75% to 125% of the scheduled applications of the assigned product for 12 weeks, do not miss more than 6 consecutive applications, return for the 12-week evaluation within +/- 4 days OR have discontinued from the study due to lack of treatment effect (after completing at least 8 weeks of compliant study medication use), and have no protocol major violations.

Patients who are discontinued prematurely from the study due to lack of treatment effect after completing at least 8 weeks of compliant study medication use and without major protocol violations will be included in the PP population as treatment failures (i.e., non-responders) even if they do not have Week 12 evaluation within the visit window or at all. An LOCF approach will be used for imputing missing lesion counts in these PP patients and they will be considered as failures in the IGE evaluations.

Patients discontinued prematurely for other reasons (including those who discontinue due to lack of treatment effect with less than 8 weeks of treatment) will be excluded from the PP population, but included in the mITT population, using LOCF.

Patients can be additionally excluded from the PP population due to non-compliance, if the Investigator's and Sponsor's review of their dosing times suggests a clinically meaningful departure from a twice-daily dosing pattern.

For the purpose of determining the PP status of the patient, a "major protocol violation" is any patient or investigator activity that could have possibly interfered with the therapeutic administration of the treatment or the precise evaluation of the treatment efficacy.

The PP population will be considered as definitive for testing the clinical equivalence and as supportive while testing the superiority.

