7.4 Protocol Deviations

Protocol deviations will be derived algorithmically. The following deviation categories will be derived:

1. Use of prohibited medication: use of any concomitant medication identified by the clinical review as critical and influencing the efficacy outcomes (major deviation).
2. Concomitant Medication – not critical: use of any other concomitant medication (minor deviation).
3. Diary accountability: subjects failing to return their diary at at least one scheduled visit (minor deviation).
4. Missed > 6 consecutive doses (major deviation).
5. IP compliance < 75% or > 125% (major deviation).
6. Dosing – Missed Doses(s): subjects who missed at least one dose, but do not fall under the previous two items (minor deviation).
7. IP Accountability: subjects who failed to return the IP at at least one scheduled visit (minor deviation).
8. Visit 4 out of window: subjects who attended Week 12 visit outside of \pm 4-day window (major deviation).

9. Failed to return to Visit 4: subjects who do not attend Visit 4 at all. This deviation will not apply to subjects who discontinued from study due to lack of treatment effect after at least 8 weeks of treatment (major deviation).
10. Inclusion/Exclusion criteria violated: subjects who were enrolled despite violating inclusion/exclusion criteria (major deviation).
11. Pregnancy: subjects with positive pregnancy test results at any time during the study or adverse event with preferred term "Pregnancy" or discontinuing from the study with reason "Pregnancy" (major deviation).
12. Urine Pregnancy Test not done: subject is female and of child-bearing potential, but UPT was not performed at Visits 2, 3, or 4 (minor deviation).
13. Facial lesion count not done at Visits 2 or 3 (minor deviation);
14. Facial lesion count not done at Visit 4 (major deviation);
15. IGE not done at Visits 2, 3, or 4 (minor deviation);
16. Sign and symptoms of local irritation not done at Visits 2, 3, or 4 (minor deviation).

Additional deviations may be reported by sites classified into deviation categories and graded as major or minor.

Protocol deviations will be summarized by deviation type and treatment group. This analysis will be performed for Safety, mITT, and PP populations.

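### Dividing every patient's compliance by 168 applications makes an adherent treatment failure stopped around Week 8 miss the 75% limit, although the plan places that patient in the per-protocol population

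*SAP*

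**What the plan says.** **Inclusion.** SAP 6.3 says that patients who stop for lack of effect "after completing at least 8 weeks of compliant study medication use and without major protocol violations will be included in the PP population" as non-responders, even without a Week 12 evaluation. SAP 7.5.2 carries their lesion counts forward and SAP 7.5.3 counts them as IGE failures. Protocol 12.4.4 gives the same handling.

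**Compliance.** SAP 7.6.3 holds the SAP's only compliance formula: recorded over planned applications, "where Planned number of applications is 168". A patient is compliant who applies "at least 75% and not more than 125% of doses, with no more than 6 consecutive missed doses". The same section counts as missed any dose between the last application and the time dose 168 would have fallen due.

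**PP entry.** The first sentence of SAP 6.3 requires PP patients to "apply 75% to 125% of the scheduled applications of the assigned product for 12 weeks". Its alternative for patients who stopped early replaces only the 12-week visit.

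**Deviations.** SAP 7.4 states "Protocol deviations will be derived algorithmically". Item 5 grades compliance outside 75% to 125% as major for everyone. Item 9, on a missed Visit 4, exempts treatment failures after 8 weeks.

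**Protocol source.** Protocol 11.8.9 judges compliance over the whole study, so the 168 follows from it. Protocol 12.4.4 likewise keeps compliance as a condition separate from its discontinuation alternative.

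**The concern.** The plan says that a late treatment failure belongs in PP, then defines compliance so that a failure stopped at about Week 8 cannot qualify, however well the product was used. One programmer could follow the 7.6.3 formula and another the failure paragraph of 6.3, and they would build different PP sets.

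PP is the definitive set for the equivalence conclusion on both endpoints, and the disputed patients are identified by poor response. Removing them raises each arm's mean reduction by an amount that depends on that arm's failure rate. If the Test arm has more failures, the ratio moves towards 1. If the Reference arm has more, it moves away.

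A related gap concerns the same group. Protocol 12.4.4 and the synopsis also put into PP patients who need alternate or supplemental rosacea therapy after eight weeks. SAP 6.3, 7.5.2 and 7.5.3 name only lack of effect, SAP 6.3 excludes those who stop for other reasons, and SAP 8 declares no changes from the Protocol.

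**Working it through.** **Reproducing the plan's figure.** Two applications a day for 84 days (SAP 3.1) give 2 × 84 = 168. The 75% limit is 0.75 × 168 = 126 applications.

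**Highest possible compliance.** The diary has one morning and one evening box per day (SAP 7.6.3), and Day 1 is the first dosing day, which may begin in the evening (Protocol 11.7.1). With no missed dose, a stop on Day d gives 2d applications after a morning start and 2d − 1 after an evening start.

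| Stop | Morning start | Evening start |
|---|---|---|
| Day 56 | 112/168 = 66.7% | 111/168 = 66.1% |
| Day 60 | 120/168 = 71.4% | 119/168 = 70.8% |
| Day 62 | 124/168 = 73.8% | 123/168 = 73.2% |
| Day 63 | 126/168 = 75.0% | 125/168 = 74.4% |
| Day 64 | 128/168 = 76.2% | 127/168 = 75.6% |

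The Visit 3 window ends on Day 60. If the first dose is on the evening of Day 0 and dosing runs through the evening of study Day 60, the count is 121/168 = 72.0%. No failure stopped at an in-window Visit 3 reaches 75%.

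**Later stops.** With a morning start, the use needed to reach 126 applications is 126/(2d): 126/140 = 90% on Day 70 and 126/154 = 81.8% on Day 77. At 80% use, 126/1.6 = 78.75, so the limit is reached only on Day 79.

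**With a prorated denominator.** A fully adherent Day 56 stop scores 112/112 = 100%. A patient using 75% scores 84/112 = 75% and is kept. Anyone below that is still excluded.

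**Effect on the ratio (assumed inputs).** The documents give 224 PP patients per arm, a Reference reduction of 55% and an SD below 47% (47 is used here). The following are assumptions: failure rate f, share of failures excluded e, and mean reduction in failures m. The retained mean is (μ − f·e·m)/(1 − f·e). At a true ratio of 0.80 the Test mean is 44. With f = 6% Test and 2% Reference, e = 1 and m = 0:

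- Test: 44/0.94 = 46.81
- Reference: 55/0.98 = 56.12
- Ratio: 0.834

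With m = 25 and e = 0.5 the ratio is 0.806. With the rates reversed (2% v 6%), the same two cases give 0.767 and 0.790.

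**False-pass probability at a true ratio of 0.80.** This was simulated with 100,000 runs per cell, overall SD 47, failure SD 20, the Fieller 90% interval within 0.80 to 1.25, pooled SD and no site term. With failures included it is 4.8% to 5.0%.

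| Failures, Test v Reference | m=0, e=1 | m=0, e=0.5 | m=25, e=1 | m=25, e=0.5 |
|---|---|---|---|---|
| 6% v 2% | 11.9% | 7.5% | 7.0% | 5.9% |
| 3% v 1% | 7.9% | 6.2% | 5.9% | 5.4% |
| 4% v 4% | 4.9% | 4.9% | 4.3% | 4.7% |
| 1% v 3% | 3.1% | 3.9% | 3.7% | 4.3% |
| 2% v 6% | 1.8% | 3.1% | 2.8% | 3.6% |

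At a true ratio of 1.00, the pass probability is 0.72 with failures included and 0.70 to 0.76 after exclusion.

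**IGE.** Excluded failures are all non-successes, so a success proportion p becomes p/(1 − f). At 6% v 2% with all excluded, the difference shifts by p × (1/0.94 − 1/0.98) = 0.0434p. That is 1.3 percentage points at p = 0.30 and 2.6 at p = 0.60.

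**The case against.** The strongest reply is that SAP 6.3 addresses exactly this patient and says that the patient is included, and that SAP 7.5.2, SAP 7.5.3 and Protocol 12.4.4 agree. Eight weeks of compliant use makes sense at Week 8 only if compliance is judged over the weeks treated. That reading is plausible and probably what was intended. But no formula in the SAP supports it, and SAP 7.6.3 points the other way: a Day 56 stop is charged the remaining 168 − 112 = 56 doses as missed.

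Some narrower points stand:

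- SAP 7.4 only says that deviations are summarized, and SAP 6.3 defines a major violation in its own words. The exclusion therefore rests on the 12-week condition in 6.3 read with the 7.6.3 formula, and item 5 only adds to it.
- The rule on consecutive missed doses stops counting at the Visit 4 date. SAP 11.1 and Protocol 11.7.4 label Visit 4 as including early discontinuation, and on that reading this second route to exclusion mostly disappears. SAP 7.4 items 8 and 9 use Visit 4 to mean Week 12, so the point is still worth a clarifying line.
- SAP 3.1 lets a worsened patient be discontinued as a treatment failure, so the SAP may mean to cover the alternate-therapy group. It does not say so.
- The simulated range includes strong imbalances between two active foams. With milder ones the false-pass probability is 5.0% to 6.4% at 3% v 2% and 5.1% to 6.2% at 4% v 3%.
- The mITT equivalence analysis keeps these patients and could reveal a divergence, although it is only supportive. Superiority is definitive in mITT and is unaffected.

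**Conclusion.** The concern holds and should be fixed before unblinding. The arithmetic is exact: on the stated denominator, a fully adherent failure stopped on Days 56 to 62 cannot reach 75%, and an evening start extends this to Day 63. No passage exempts these patients. Followed as written, the formula removes from the definitive equivalence set patients whom the Protocol and SAP say belong in it, and it does so by outcome.

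The effect on the equivalence result cannot be estimated from the documents, because they give no failure rate. Over the tabulated assumptions the false-pass probability ranges from 1.8% to 11.9%, against about 5% with failures included, and the direction depends on which arm has more failures. The upper end needs a threefold imbalance, every failure excluded and no mean improvement among them. The IGE shift is small against the 0.20 margin. The case for a change is therefore the contradiction over who enters the analysis set. It does not rest on a demonstrated large bias.

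**What to change.** - **SAP 7.6.3:** for patients discontinued for lack of effect after at least 8 weeks, use as denominator the applications scheduled from first dose to discontinuation, and count missed and consecutive missed doses only to that date. Name the date explicitly (recorded discontinuation date or last application), because rest periods can separate the two.
- **SAP 6.3 and 7.4:** state that the 75% to 125% condition and items 4 and 5 are assessed on that basis for these patients, and that the early discontinuation visit is the Visit 4 date for the consecutive-dose rule.
- **Protocol 11.8.9:** reconcile its whole-study wording with the rule above.
- **Alternate or supplemental therapy patients:** state that the SAP's failure group includes them, as the Protocol does, or list the difference in SAP 8.

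These are analysis-set rules only. The cost is a few lines of SAP text and derivation code. Diary counts, first-dose time and discontinuation dates are already collected. A revision of Protocol 11.8.9 would also need the Sponsor and IRB approvals in Protocol 14.7. PP means may be slightly less favourable because failures stay in.
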